6.3 Steps to Determine If an Adverse Event Requires Expedited Reporting

Step 1: Identify the type of adverse event

Step 2: Grade the adverse event

Step 3: Determine whether the adverse event is related to the protocol therapy

Attribution categories are as follows:

- Definite – The AE is *clearly related* to the study treatment.
- Probable – The AE is *likely related* to the study treatment.
- Possible – The AE *may be related* to the study treatment.
- Unrelated – The AE is *clearly NOT related* to the study treatment.

Step 4: Determine the prior experience of the adverse event.

Expected events are those that have been previously identified as resulting from administration of the agent. An adverse event is considered unexpected, for expedited reporting purposes only, when either the type of event or the severity of the event is not listed in:

- the current known adverse events listed in the Agent Information Section of this protocol;
- the drug package insert;
- the current Investigator's Brochure

6.4 Reporting Requirements for Adverse Events

6.4.1 Expedited Reporting

- The Principal Investigator will be notified within 24 hours of learning of any serious adverse events, regardless of attribution, occurring during the study or within 30 days of the last administration of the study drug.
- The University of Pennsylvania IRB must be notified within 10 business days of "any unanticipated problems involving risk to subjects or others" (UPR/UPIRSO).

The following events meet the definition of UPR:

1. Any serious event (injuries, side effects, deaths or other problems), which in the opinion of the Principal Investigator was unanticipated, involved risk to subjects or others, and was possibly related to the research procedures.
2. Any serious accidental or unintentional change to the IRB-approved protocol that alters the level of risk.
3. Any deviation from the protocol taken without prior IRB review to eliminate apparent immediate hazard to a research subject.

4. Any new information (e.g., publication, safety monitoring report, updated sponsor safety report), interim result or other finding that indicates an unexpected change to the risk/benefit ratio for the research.
5. Any breach in confidentiality that may involve risk to the subject or others.
6. Any complaint of a subject that indicates an unanticipated risk or that cannot be resolved by the Principal Investigator.

6.4.2 Routine Reporting

All other adverse events- such as those that are expected, or are unlikely or definitely not related to the study participation- are to be reported annually as part of regular data submission.

6.5 Stopping Rules

This study does not have a primary safety endpoint or place study subjects at high risk.

7 DRUG/DEVICE INFORMATION

7.1 Propranolol hydrochloride

- Other names for the drug: Inderal
- Classification - type of agent: β -blocker, antiarrhythmic
- Mode of action: Propranolol is a nonselective beta-adrenergic receptor blocking agent that specifically competes with beta-adrenergic receptor stimulating agents for available receptor sites, thereby decreasing chronotropic, inotropic, and vasodilator responses to beta-adrenergic stimulation.
- Protocol dose: 2mg IV; one possible repeat dose \geq 2 hours later
- Route of administration for this study: IV push
- Incompatibilities: there are no medications that are contraindicated for use with propranolol
- Availability: commercially available, on formulary
- Side effects: hypotension, congestive heart failure, bradycardia, heart block, cardiac arrest, bronchospasm, and cutaneous ulcers. (Please refer to the manufacturer's package insert for a complete list of adverse events)
- Nursing implications: Propranolol is excreted in breast milk.

7.2 Product Preparation/Packaging, Receipt and Storage

Investigational Drug Service (IDS) of the University of Pennsylvania will purchase commercial propranolol hydrochloride 2mg/mL vials. An internal lot number and use-by date will be assigned. Visually-matching placebo vials of normal saline 0.9% will be purchased by IDS. An internal lot number and use-by date will be assigned.

IDS will dispense pre-randomized and numbered packets of study medication containing two doses of either propranolol or placebo medication. IDS will package and deliver the drugs to the locked labor floor medication room. Drug accountability will be maintained by IDS and study coordinators.

Study medication and placebo will be stored at room temperature in the locked medication room on the labor floor only accessible by floor and research staff.

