Propranolol Rescue of Prolonged Labor (PROPEL)

A randomized, double-blind, placebo-controlled multicenter investigation of propranolol's effect on cesarean delivery rate among women with prolonged labor

Principal Investigator: [name], MSCE

Assistant Professor

Division of Maternal Fetal Medicine

Department of Obstetrics and Gynecology

[name]

[name]

[name]

Sub-Investigator(s): [name]

Clinical Fellow

Division of Maternal Fetal Medicine

[figure not shown]
Department of Obstetrics and Gynecology

Study Drug/Study Device: Propranolol hydrochloride

LIST OF ABBREVIATIONS

AE	Adverse event
DSMB	Data safety monitoring board
CD	Cesarean delivery
EFM	Electronic fetal monitoring
GBS	Group B streptococcus
HIE	Hypoxic ischemic encephalopathy
ICN	Intensive care nursery
ICU	Intensive care unit
IDS	Investigational drug service
IOL	Induction of labor
IRB	Investigational review board
IV	Intravenous
IVH	Intraventricular hemorrhage
NEC	Necrotizing enterocolitis
OB	Obstetric
RDS	Respiratory distress syndrome
SAE	Serious adverse event
VTE	Venous thromboembolism

STUDY SCHEMA

Study Summary

Title	Propranolol rescue of prolonged labor
Short Title	PROPEL
Methodology	Double-blind randomized controlled trial
Study duration	24 Months
Study Center (s)	Multi-center: Hospital of the University of Pennsylvania and Pennsylvania Hospital
Objective	To compare cesarean delivery (CD) rates in women given IV propranolol versus placebo for treatment of prolonged labor.
Number of Subjects	326
Diagnosis and Main Inclusion Criteria	
Meets criteria for prolonged labor:
 
 1. cervical dilation <6 cm after \geq12 hours with ruptured membranes and receiving oxytocin OR 2. cervical dilation >6 cm and <1 cm dilation change over \geq2 hours with ruptured membranes and receiving oxytocin 
AND
 
\geq16 years old, \geq 36 weeks gestation; Singleton gestation in vertex presentation; non anomalous fetus

Study Product (s), Dose, Route, Regimen	
IV Propranolol – 2mg; one possible repeat dose \geq2 hours later
 
Normal saline placebo- 2 mL; one possible repeat dose \geq2 hours later

Duration of administration	Eligible for maximum of one repeat dose \geq 2 hours after first until reaches 10cm dilation
Primary Outcome	Cesarean delivery
Statistical methodology	Intention to treat analysis, chi-square test for categorical variables, two-sample t-test for continuous variables

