4 TREATMENT ARMS

4.1 Treatment Dosage and Administration

- Propranolol hydrochloride 2mg IV
 - One possible repeat dose of 2mg IV given ≥ 2 hours later if < 2 cm cervical dilation change over > 2 hours on subsequent exam
- Placebo – 2mL of 1% normal saline solution IV
 - One possible repeat dose of 2mL IV given ≥ 2 hours later if < 2 cm cervical dilation change over > 2 hours on subsequent exam

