5.2 Randomization

Eligible, consented women will receive pre-randomized study medication. Study medications will be prepared and randomized by the Investigational Drug Service (IDS) via a random generated randomization scheme. The randomization scheme will be generated by a pharmacy associate within IDS not involved in the clinical care of the patient. Two single-use vials of the same medication – either propranolol or placebo- will be included in a numbered bag. One vial will be used for the first dose. If a patient meets eligibility criteria to receive a repeat dose, the second vial in the same bag will be used.

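### A 2 mg propranolol dose from 2 mg/mL vials is 1 mL, the placebo dose is 2 mL, and no common injection volume is stated

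*Combined protocol and SAP*

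**What the plan says.** The active dose is given only by mass. Section 4.1 has "Propranolol hydrochloride 2mg IV", section 7.1 has "Protocol dose: 2mg IV", and the study summary agrees. The route in 7.1 is "Route of administration for this study: IV push". For supply, section 7.2 says IDS "will purchase commercial propranolol hydrochloride 2mg/mL vials".

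The placebo dose is given only by volume. The study summary has "Normal saline placebo- 2 mL" and section 4.1 has "2mL of 1% normal saline solution IV".

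The packaging text bears on how these figures meet at the bedside. Section 5.2 puts "Two single-use vials of the same medication" in each numbered bag, one for the first dose and the other for a possible repeat. Section 7.2 adds "Visually-matching placebo vials of normal saline 0.9% will be purchased by IDS". Section 4.7 blinds physicians, staff and patients.

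**The concern.** The two arms are dosed in different units, and the one concentration that links them does not make the volumes equal. Staff who are blinded and hold a numbered bag need a single volume that serves both arms. The protocol never states one, and the volumes its figures imply differ.

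The blind matters more than usual here. The primary endpoint is cesarean delivery, and section 3.4 leaves the indications for cesarean to the obstetric provider. A visible difference between the arms in the vial or syringe is the kind of cue that the double-blind design is meant to remove. Section 9.5 also asks that, emergencies aside, the trial be run as the protocol describes, so the operative dosing figures should be ones that can be followed together.

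**Working it through.** **Inputs**
- Active dose: 2 mg (study summary, 4.1, 7.1)
- Propranolol concentration: 2 mg/mL (7.2)
- Placebo dose: 2 mL (study summary, 4.1)
- Vials: one single-use vial per dose (5.2), placebo visually matched (7.2)
- Rate limit cited from the package insert: 1 mg per minute (1.2)

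**Can the 2 mL figure be reproduced for the active arm?**
Volume = dose / concentration = 2 mg / (2 mg/mL) = 1 mL. It cannot. The ratio of placebo to active volume is 2 mL / 1 mL = 2. Over two doses it is 2 × 2 = 4 mL against 2 × 1 = 2 mL, the same ratio.

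**What concentration would reproduce it?**
2 mg / 2 mL = 1 mg/mL, half the concentration in 7.2. No section states this concentration or a dilution to reach it.

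**Which statements survive each possible reading?**

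| Reading | Active | Placebo | What it keeps | What it contradicts |
|---|---|---|---|---|
| A | 1 mL at 2 mg/mL | 1 mL | 2 mg dose, 7.2 concentration, equal volumes | 2 mL placebo in the summary and 4.1 |
| B | 2 mL at 1 mg/mL | 2 mL | 2 mg dose, 2 mL placebo, equal volumes | 2 mg/mL in 7.2, unless diluted (no dilution stated) |
| C | 1 mL at 2 mg/mL | 2 mL | all three stated figures | equal volumes, and so a full match between arms |
| D | 2 mL at 2 mg/mL | 2 mL | 7.2 concentration, 2 mL placebo, equal volumes | 2 mg dose: 2 mL × 2 mg/mL = 4 mg |

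No reading keeps everything. A and B each need one stated figure to be a slip or an unstated dilution. C keeps every figure but gives up equal volumes. D changes the dose. The documents do not say which was meant.

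**Injection time**
2 mg / (1 mg/min) = 2 minutes at least, whether the 2 mg is in 1 mL or in 2 mL. The cited rate limit therefore does not favor either volume.

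**The case against.** The best defense is the packaging. IDS prepares the bags, each bag holds two vials for two doses, and one vial is used each time. No section asks bedside staff to measure a volume, and staff who do not know the arm could not apply an arm-specific one. A volume cue then arises only if the vials are filled unequally, and visual matching points against that. On this view the blind is protected and all that remains is a slip in one figure.

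Most of this stands. It makes any threat to the blind conditional on unequal fill or injected volumes. It does not remove the inconsistency: visual matching is a statement about appearance, fill volume is not given, and equal filling at either volume contradicts a figure stated elsewhere. The text needs correcting whichever figure was intended.

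Two stronger readings are tempting. A reader might infer that the blind fails and the cesarean result is biased. The documents do not support this. Section 5.3 has the clinician fetch the bag and the nurse use the second vial, but does not say who injects the first dose, so it is unknown whether a cue would reach the person deciding on cesarean. A reader might also infer a 4 mg overdose, above the usual 1 to 3 mg quoted in 1.2. That needs a propranolol vial holding more than one 2 mg dose. No section describes such a vial, and none tells staff to inject 2 mL of the 2 mg/mL solution.

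**Conclusion.** The inconsistency is certain and rests on division alone: 1 mL of propranolol against 2 mL of placebo per dose, a twofold difference that no section resolves. It lies in operative dosing text, so it should be corrected.

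The consequence is conditional. If fill or injected volumes follow the stated figures, whoever handles the dose has a cue to allocation. If the pharmacy equalizes them, the blind is kept and only the wording is wrong. The documents do not settle which. Actual unblinding is not shown, and there is no basis for a figure on bias in the cesarean rate. The sample size and the planned analysis are unaffected.

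Two nearby drafting points would not merit a comment alone. Section 4.1 calls the placebo 1% saline where 7.2 says 0.9%. Section 1.2 cites the rate limit, but 5.3 and 7.1 give no injection time. The statement of compliance in 1.2 follows the sentence on second-dose timing, so it may not have been meant to cover the rate.

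**What to change.** State one concentration and one volume, per vial and per dose, for both arms in the study summary, 4.1 and 7.2. Either option works:

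1. **1 mL in both arms:** propranolol 2 mg/mL against 1 mL of 0.9% saline. No dilution is needed.
2. **2 mL in both arms:** propranolol 1 mg/mL, supplied at that strength or diluted by IDS, against 2 mL of 0.9% saline.

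Option 1 is simpler if the 2 mg/mL vials in 7.2 are correct. In the same edit, change the saline in 4.1 to 0.9%, and specify in 5.3 and 7.1 that the IV push takes at least 2 minutes in both arms, in line with the limit cited in 1.2.

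The cost is text changes in five places (study summary, 4.1, 5.3, 7.1, 7.2), plus an IDS dilution step only if option 2 is chosen with 2 mg/mL vials. No extra participants or study procedures are needed.

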8 STUDY DESIGN/STUDY ENDPOINTS

This will be a prospective, double-blind, placebo-controlled, randomized, multi-center study on the effect of propranolol versus placebo on the rate of cesarean delivery for women with prolonged labor. Please refer to section 2.3 for endpoints.

Regarding stopping rules for safety or efficacy, we do not anticipate early termination of the study for either. Issues that would be of concern would be persistent bradycardia or hypotension with therapy and unexpected events. Other findings that could trigger a safety review include the number of SAEs overall, the number of occurrences of a particular type of SAE, severe AEs, or increased frequency of events.

8.1 Sample Size and Accrual

The sample size is based on the expected CD rate for women experiencing prolonged labor of approximately 45%. For a power of 80% and an alpha of 0.05, 326 women would be needed to find a decrease in rate of CD to 30%.

We estimate 40 eligible women deliver at HUP per month. We anticipate approaching 80% of these women or approximately 32 per month. With an estimated 50% consent rate, we would enroll approximately 16 women per month. Therefore, we would need 24 months to reach our target enrollment of 326 women.

8.2 Data Analyses Plans

Measures of relative risk will include 95% confidence intervals. Descriptive statistics will be presented as mean with standard deviation, median with interquartile range, or proportion with 95% confidence interval based on data type and distribution. Comparisons between groups will be performed using a Chi-square or Fisher's exact test for categorical variables and parametric or non-parametric tests for continuous variables, as appropriate. Intention-to-treat analyses will be conducted such that all patients with available follow-up measures will be included in the analysis. Statistical analyses were conducted in STATA, version 15.1 (College Station, Texas). Two-tailed P values of <0.05 will be considered statistically significant.

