3.1 Inclusion Criteria

English-speaking

≥ 16 years of age

≥ 36 weeks gestation

Singleton pregnancy

Vertex presentation

No contraindication to a vaginal delivery

Meets at least one study criteria for prolonged labor:

1. cervical dilation <6 cm after ≥12 hours with ruptured membranes and receiving oxytocin

OR

2. cervical dilation >6 cm and <1 cm dilation change over ≥2 hours with ruptured membranes and receiving oxytocin

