5 STUDY PROCEDURES

5.1 Screening for Recruitment and Recruitment Process

Women meeting the criteria listed in section 3.1 will be invited to participate in the study and written informed consent will be obtained from those who choose to participate. The screening procedures include:

- Informed Consent
- Medical history: Complete medical and surgical history
- Demographics: Age, gender, race, ethnicity
- Review subject eligibility criteria
- Review previous and concomitant medications
- Physical exam including vital signs, height and weight
- Vital signs (temperature, pulse, respirations, blood pressure), height, weight
- Adverse event assessment: Baseline adverse events will be assessed. See section 6 for Adverse Event monitoring and reporting.

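### Optional free improvement: the unadjusted primary cesarean comparison is valid, but pre-specified adjustment for parity and the qualifying entry criterion could add about 0 to 3.6 points of power at N=326

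*Combined protocol and SAP*

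**What the plan says.** The primary endpoint is cesarean versus vaginal delivery (section 2.2.1). The Study Summary gives the method as "Intention to treat analysis, chi-square test for categorical variables". Section 8.2 repeats this in general terms, "Comparisons between groups will be performed using a Chi-square or Fisher's exact test for categorical variables", and adds that "Measures of relative risk will include 95% confidence intervals". Neither place names a covariate or an adjusted model.

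Section 8.1 assumes a cesarean rate of about 45% and states that "326 women would be needed to find a decrease in rate of CD to 30" per cent, with 80% power and alpha 0.05. Section 5.2 describes allocation only as "via a random generated randomization scheme" and names no stratification factor.

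Section 3.1 admits women by either of two routes: "cervical dilation <6 cm after" 12 hours or more, or "cervical dilation >6 cm and <1 cm dilation change over" 2 hours or more, both with ruptured membranes and oxytocin running. Eligibility is checked at screening (section 5.1: "Review subject eligibility criteria"), so the route of entry is known before treatment. Section 9.2 plans to record obstetrical and medical history. Parity would ordinarily fall under that heading but is not named, and no section says that the qualifying criterion is kept as a data field. Section 9.2.2 provides for chart review.

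**The concern.** In a randomized trial with a binary outcome, adjusting for baseline factors that predict the outcome narrows the confidence interval for the same overall risk difference and risk ratio. A woman below 6 cm after at least 12 hours and a woman stalled beyond 6 cm may well differ in their chance of cesarean, as may nulliparous and parous women. If so, the plan gives up some precision that it could have without extra participants or examinations. At stake is a modest amount of power in a trial sized for 80%, not the validity of its result.

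**Working it through.** **1. The plan's own figure.** Inputs from sections 8.1 and 8.2: p1 = 0.45, p2 = 0.30, two-sided alpha 0.05, power 80%. Equal allocation is assumed, since no ratio is stated. With pooled rate 0.375:

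n per arm = [1.960 × √(2 × 0.375 × 0.625) + 0.842 × √(0.45 × 0.55 + 0.30 × 0.70)]² / 0.15² = (1.342 + 0.569)² / 0.0225 = 162.3

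This rounds up to 163 per arm, or 326 in total, as stated. At 163 per arm, power is 80.2% by the formula and 80.1% by exact binomial calculation for the uncorrected chi-square. The exact type I error of that test is 4.9 to 5.1% for common rates of 30 to 45%. The planned test is therefore valid and matches its sample size.

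**2. Assumptions for adjustment (none of them in the documents).** 60% nulliparous, 50% entering below 6 cm, the two factors independent, and additive effects of d1 (parity) and d2 (criterion) on the cesarean rate. The share of outcome variance explained is

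R² = (0.24 d1² + 0.25 d2²) / (0.375 × 0.625)

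For 15/10 points this is (0.0054 + 0.0025) / 0.2344 = 0.034. For 25/15 it is (0.0150 + 0.0056) / 0.2344 = 0.088.

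**3. Power at 163 per arm.** The formula column multiplies both standard errors, 0.0536 (null) and 0.0530 (alternative), by f = √(1 − R²): power = Φ[(0.15 − 1.960 × 0.0536 f) / (0.0530 f)]. The simulated columns use 200,000 trials per setting. The model is a logistic regression on arm, parity and criterion, and the test is on the standardized risk difference with an influence-function standard error. The calibrated column resets the critical value so that the adjusted test has exactly 5% type I error with both arms at 37.5%. Net gain is calibrated power minus the 80.0% that the calibrated test has at 0/0.

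| Effect, parity/criterion (points) | Treated-arm cell rates | R² | Formula power (gain) | Chi-square | Adjusted | Adjusted, calibrated | Net gain |
|---|---|---|---|---|---|---|---|
| 0/0 | 30% | 0 | 80.2% (0) | 80.1% | 80.5% | 80.0% | 0 |
| 5/5 | 24.5 to 34.5% | 0.005 | 80.4% (0.2) | 80.1% | 80.7% | 80.1% | 0.1 |
| 15/10 | 16 to 41% | 0.034 | 81.5% (1.3) | 80.0% | 81.8% | 81.4% | 1.4 |
| 20/10 | 13 to 43% | 0.052 | 82.2% (2.0) | 80.0% | 82.4% | 82.0% | 2.0 |
| 25/15 | 7.5 to 47.5% | 0.088 | 83.7% (3.5) | 80.1% | 84.1% | 83.6% | 3.6 |

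The 0/0 row shows why calibration matters. With uninformative covariates the adjusted test still appears to gain 80.5 − 80.1 = 0.4 point, purely because the Wald test is slightly liberal. The formula and the calibrated simulation agree on what is left.

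**4. Precision.** The width of the 95% interval for the risk difference falls from about 20.8 points to 20.4 (15/10) or 19.8 (25/15).

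**5. Error rate and robustness.** The adjusted risk-difference test has a type I error of 5.1 to 5.3%. With the criterion missing for 30% of women and set to the most frequent category, uncalibrated power is 81.7% (15/10) and 83.6% (25/15). With parity alone it is 81.4% and 83.0%. Against the 80.5% baseline that is 0.9 of 1.3 points and 2.5 of 3.6 points, or about 70% of the gain. The model failed to converge in at most 2 of 200,000 trials.

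**The case against.** The strongest reply is that nothing is wrong. An unadjusted test of a randomized binary outcome is a sound choice, and the gain rests entirely on inputs that the documents lack. That stands, and it is why this is an option with a range that starts at zero. The upper end also needs strong predictors: 25/15 implies treated-arm cesarean rates running from 7.5% to 47.5%.

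The change also has a price. Section 8.2 names relative risk as its measure, and here the risk difference would decide. The adjusted risk-ratio test would have 79.6% power at 0/0 and 79.8% at 5/5, slightly below the chi-square. The two scales give different decisions in 0.6 to 0.9% of simulated trials, so one has to be named in advance. This stands as a small cost to be stated.

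Three stronger readings are tempting but unsupported:
- **The planned analysis is invalid or the trial is underpowered.** Step 1 shows neither. Section 8.1 adds no allowance for dropout, but mode of delivery is known at the delivery itself, so little loss of the primary outcome is to be expected.
- **The gain is a full 4 points.** The raw difference at 25/15 (84.1 − 80.1) includes the 0.4 point of test liberality, which needs no covariates.
- **The mention of Fisher's exact test in 8.2 costs power.** The Study Summary names chi-square, and about 163 × 0.375 = 61 cesareans are expected per arm, so there is no reason to expect Fisher's test to be used for the primary outcome.

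**Conclusion.** The point holds as a free improvement and not as an error. Adjusting for parity and the qualifying criterion would add about 0 to 3.6 points of power at N=326, net of test liberality. This rests on equal allocation, the assumed mix of women, and additive effects between 0/0 and 25/15 points. The documents do not say where in that range the trial lies. If the factors are not prognostic, power is essentially unchanged. The sponsor can reasonably decline.

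**What to change.** Add to section 8.2, before unblinding, a paragraph to this effect:

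> The primary analysis is a logistic regression of cesarean delivery on arm, parity (nulliparous or parous) and qualifying entry criterion. The standardized risk difference, with its two-sided p-value and 95% confidence interval, decides the primary hypothesis at 0.05 (Stata: logit with vce(robust), then margins with vce(unconditional)). The standardized risk ratio with 95% confidence interval is also reported and does not decide. A woman with a missing covariate is kept and assigned the most frequent category, chosen blind to arm. The unadjusted chi-square without continuity correction is supporting, and decides only if the model does not converge.

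Make parity and the qualifying criterion REDCap fields, filled by chart review for women already enrolled. A dilation of exactly 6 cm meets neither criterion in section 3.1, so the sponsor must reconcile that section before the criterion can be coded. If that is not done, adjust for parity alone, which keeps about 70% of the gain. Hospital is left out because the documents give no basis for its value.

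The cost is one paragraph and two fields, with no added participants, visits or examinations. The plan should also acknowledge the type I error of about 5.1 to 5.3% and that the relative risk no longer decides.

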of IV propranolol to nulliparous women admitted for labor or for induction of labor (IOL).⁸ Notably, these patients did not have any diagnosis of dystocia, and the medication was given as an adjunct to normal labor management. The CD rate was quite low overall in this study, and there was no significant difference between the two groups. Another study was a double-blind RCT of women with arrest of dilation, with an unchanged cervical exam for 2 hrs anywhere from 2-7cm during labor.⁷ Patients received 2mg IV propranolol with a repeat dose in 1 hr if unchanged, vs placebo. This study also had a low overall CD rate, with no difference between groups. Two additional studies have evaluated the use of propranolol as an induction agent.^{4,6} Both were done in Iran where the induction protocol is quite different than in the US. The first study, which included only nulliparous patients, showed no difference in CD rate but a 2.5 hour shorter time to delivery; the second study found a significant difference in CD rate from 40 to 20% in the PO propranolol group. Finally, one additional study evaluated the administration of propranolol to women with arrest of active phase but with a low rate of oxytocin usage – 28% of propranolol the group versus 60% of placebo group.⁵ Ultimately this study showed no difference in the CD rate, but given the low use of oxytocin in this study, it is less applicable to most obstetric practice. In the 7 total published clinical trials referenced above, there were no reported safety issues, side effects, or incidences of worse maternal or neonatal outcomes in those patients who received propranolol. Each of the 7 trials demonstrated the safety of administering this medication in labor.

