2.2 Endpoints

2.2.1 Primary Endpoint

- Mode of delivery (cesarean versus vaginal)

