2.2.2 Secondary Endpoints

- Time (hours) from start of labor/IOL to delivery

- Time (hours) from study drug administration to delivery
- Time (hours) from start of second stage of labor to delivery
- Indication for CD
- Operative vaginal delivery
- Cumulative and maximum dose of intrapartum oxytocin received
- Postpartum hemorrhage
- Maternal blood transfusion
- Endometritis
- Chorioamnionitis
- Wound infection
- Other composite maternal morbidity: VTE, Hysterectomy, ICU admission, Maternal readmission within 7 days and 4 weeks, Maternal death
- ICN adm > 48 hours
- Composite neonatal outcome: neonatal blood transfusion, HIE, IVH grade 3 or 4, head cooling, severe RDS, NEC, Sepsis, Death

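### Section 8.2 gives about 15 secondary measures the same unadjusted P<0.05 significance label as the primary outcome; an inert drug would earn it at least once roughly a third to a half of the time

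*Combined protocol and SAP*

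**What the plan says.** Section 2.2.1 names one primary endpoint, mode of delivery. Section 2.2.2 lists 14 secondary items under a separate heading. One of them, "Cumulative and maximum dose of intrapartum oxytocin received", holds two measures, so the list yields 15 comparisons.

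Section 8.2 is the only section that sets out the analysis in detail. It says "Comparisons between groups will be performed using a Chi-square" or Fisher's exact test for categorical variables, and parametric or non-parametric tests for continuous ones. It then closes with the rule "Two-tailed P values of <0.05 will be considered statistically significant". Nothing in that sentence or near it restricts the rule to the primary endpoint. No section gives a multiplicity adjustment or a testing order, or describes the secondary results as exploratory or descriptive.

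Two further statements matter. The sample size in section 8.1 attaches its alpha to cesarean delivery alone: "For a power of 80% and an alpha of 0.05, 326 women would be needed" to detect a fall from 45% to 30%. Section 8.2 also already promises 95% confidence intervals for relative risks and for proportions.

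**The concern.** One threshold used about 15 times without adjustment does not hold the chance of a false claim at 5% for the set of secondaries. The rule as written instructs the analyst to attach the significance label to any of them that falls below 0.05.

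The practical risk arises when cesarean delivery shows no difference. That is a realistic outcome: at 80% power the trial misses the planned effect about one time in five, and the effect may be smaller than planned. A chance result on a labor duration, oxytocin dose or operative delivery could then be reported as a significant benefit. Section 1.2 describes a previous induction trial with this pattern: no difference in cesarean rate, but a 2.5-hour shorter time to delivery.

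The same rule serves the harm outcomes poorly for the opposite reason. Several are likely to be uncommon. With about 163 women per arm, a real increase could easily fail to reach P<0.05, and the rule gives the reader only the label significant or not.

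**Working it through.** **Inputs from the documents.** Two-sided 0.05 (8.2); 326 women, 45% versus 30%, 80% power (8.1); one primary endpoint (2.2.1); 14 secondary items, 15 measures (2.2.2); chi-square or Fisher's test for categorical outcomes (8.2); no interim analysis (9.4.1).

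**Assumptions.** 1:1 allocation, since the ratio is not stated, so 163 per arm; no dropout. The documents give no secondary event rates or correlations, so ranges are used.

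**Step 1: the plan's own figure.** With the pooled-variance formula and mean rate 0.375:

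n per arm = [1.960·√(2·0.375·0.625) + 0.842·√(0.45·0.55 + 0.30·0.70)]² / 0.15² = 162.3, rounded up to 163, or 326 in total.

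This matches 8.1 exactly; power at 163 per arm is 80.2%. The whole of the 0.05 is therefore used by one comparison.

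**Step 2: independent tests, each at exactly 5%.** The chance of at least one false positive among k tests is 1 − 0.95^k.

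- 14 tests: 51.2%
- 15 tests: 53.7%
- 16 tests (two readmission windows tested separately): 56.0%

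**Step 3: rare outcomes.** Fisher's test runs well below 5% when events are few. At 163 per arm its actual error rate is about 0.3% for a 1% event rate and 1.3% for a 2% rate.

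**Step 4: correlation.** The three labor durations all end at delivery and the two oxytocin measures are related. Fifteen null endpoints were simulated in 326 women (4,000 runs per cell). The five time and oxytocin measures and the indication for cesarean were treated as tests at 5%. The other nine were binary, tested by Fisher's test when the expected count was below 5 and by chi-square otherwise. Assumed event rates were 3–20% (higher), 2–20% (middle) and 1–15% (lower). Each column gives the correlation overall, then within the time and oxytocin block.

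| Event rates | 0 / 0 | 0.1 / 0.5 | 0.3 / 0.7 | 0.5 / 0.8 |
|---|---|---|---|---|
| Higher | 52% | 48% | 45% | 41% |
| Middle | 46% | 44% | 41% | 36% |
| Lower | 42% | 39% | 37% | 33% |

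The entries run from about one third to about one half.

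**Step 5: non-harm secondaries only.** Eight of the 15 are harms: hemorrhage, maternal transfusion, endometritis, chorioamnionitis, wound infection, the maternal composite, nursery admission and the neonatal composite. Seven remain: three durations, indication for cesarean, operative vaginal delivery and two oxytocin measures. Independent: 1 − 0.95^7 = 30.2%. With correlations of 0.1/0.5, 0.3/0.7 and 0.5/0.8 it is 26%, 22% and 19%, so about 20% to 30%.

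**Step 6: power for harms.** Exact power to detect a doubling at 163 per arm (baseline rates assumed):

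| Doubling | Fisher if expected count <5, else chi-square | Fisher throughout |
|---|---|---|
| 1% to 2% | 3% | 3% |
| 2% to 4% | 14% | 10% |
| 5% to 10% | 40% | 32% |

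**The case against.** The plan does set a hierarchy. Section 2.1 has one aim, cesarean delivery; 2.2.1 has one primary endpoint; the secondaries stand under their own heading; and 8.1 ties alpha to cesarean delivery. The last sentence of 8.2 can be read as an ordinary reporting threshold, and a reader of the results can see how many secondaries were tested. Intervals are already planned for relative risks and proportions. Safety oversight runs through event-level reporting and a monitoring board (sections 5.6, 6 and 9.4.1), not through P values.

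Most of this stands, and it limits the point. Four stronger readings are tempting but not supported:

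- *That secondaries rank equally with cesarean delivery.* The hierarchy above contradicts this, and no section lets a secondary result rescue a null primary.
- *That the chance of a false secondary claim is simply one half or more.* That needs independent tests, each at exactly 5%, and the endpoint list does not fit that description.
- *That the primary error rate is inflated.* There is one primary comparison and no planned interim analysis.
- *That the plan will read a non-significant harm as safety.* Section 1.2 says of previous trials "Each of the 7 trials demonstrated the safety of administering this medication in labor", but that is background and not an analysis rule for this trial.

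The objection does not remove the wording itself. A hierarchy of endpoints does not say how secondary P values are to be interpreted, and the only sentence that does say so awards the significance label without limit.

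**Conclusion.** The point holds as a defect in a stated rule, of modest consequence. Section 8.2 labels any secondary comparison with P<0.05 as significant, without multiplicity control or an exploratory label. With an inert drug, at least one of 15 measures would earn that label with a probability of up to about 54% under independence, and roughly one third to one half under the assumed correlations and event rates. Even the low end is more than six times the nominal 5% (33/5 = 6.6). For the seven non-harm secondaries, where a false claim of benefit matters most, it is about 20% to 30%.

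Only the 54% follows from the documents' own count and threshold. The lower figures rest on rates and correlations that the documents do not give, and the harm-power figures rest on assumed baseline rates. All simulated and power figures assume 1:1 allocation. The primary comparison and the sample size stand as they are. This is a cheap improvement to the text.

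**What to change.** Replace the last sentence of section 8.2 with:

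> The two-sided 0.05 significance level applies to the single primary comparison (cesarean delivery). Secondary outcomes are reported as effect estimates with 95% confidence intervals, without multiplicity adjustment, and are not declared statistically significant. For maternal and neonatal harm outcomes, risk differences with 95% confidence intervals are given, and a non-significant P value is not taken as evidence of no harm.

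This extends the intervals that 8.2 already plans to differences in continuous outcomes and to risk differences for harms. It puts no multiplicity penalty on harm outcomes, so no safety signal is made harder to see.

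The cost is one change of wording, with no new data, patients or procedures. The downside is that the sponsor gives up the significance label for secondary findings. The change should be made before treatment allocations are unblinded for analysis.
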